#### 10.10.2 Secondary PUL

A subject undergoing a procedure for UroLift implant removal (misplaced) or additional implant(s) placement will remain on their original follow-up visit schedule.

#### 10.11 Treatment Failure

The early TWOC primary assessment is the standard data point to demonstrate urinary retention relief, however, does not consider long term durability. An independent urologist will review the outcomes of each subject and adjudicate if considered a treatment failure. The following outcomes will be reviewed to determine if a treatment failure:

- (1) The number of successful and/ or failed TWOCs.
- (2) Duration of dependence on indwelling catheter.
- (3) Prescribed surgical intervention.

#### 10.12 Subject Follow-up Rate

Investigative centres and Sponsor will collaborate to implement robust methods to retain subjects through their 12 months study visit. Appropriate management of the prospective clinical trial, proper screening of study subjects, and training of participating investigators, monitors, and study coordinators will mitigate the amount of missing data.

#### 10.13 Protocol deviations

Throughout the conduct of the study, data will be reviewed by Sponsor for the presence of deviations. Study personnel will report any deviation from the study protocol or regulation upon occurrence. The EDC will facilitate comprehensive deviation reporting through programmed edit checks which will trigger a protocol deviation eCRF. Sponsor monitors will also review data and conduct for any deviations during on-site visits per the monitoring plan. Reporting deviations in this study will be important not only for parsing the per protocol analysis, to assess quality of study conduct, but also to detect areas that should be modified for a larger study.

The Sponsor will evaluate PD trends in relation to prevention: methods of mitigation or value of requirement to the goal and study scientific integrity. Any individual site with high deviation rate will be investigated for root cause, and preventative measures will be implemented.

Any serious breaches of the Protocol, or the conditions and principles of GCP in connection to this trial, will be reported to the Ethics Committee. A serious breach is likely to effect to a significant degree – (a) the safety or physical or mental integrity of the subjects of the trial; or (b) the scientific value of the trial.

**Table 7 Schedule of Procedures**

Tests and Assessments	Screening	Index Procedure Through Release	Clinic Visit Post-procedure (3 days ± 1 day)	Clinic Visit 6 Weeks (± 7 days)	Clinic Visit 3 Months (± 14 days)	Phone Visit  6 Month (± 14 days)	Clinic Visit 12 Months (± 30 days)	Study Exit
Informed Consent must be documented prior to any procedures outside standard of care				Urinary Symptoms and UA are not required if subject is on current indwelling catheter.				
Subject Questionnaires								
Urinary Symptoms				X	X	X	X	
SHIM	If sexually active within the last 6			If sexually active at baseline	If sexually active at baseline		If sexually active at baseline	
Incontinence Severity Index				If reported	If reported	If reported	If reported	
Dysuria				If reported	If reported	If reported	If reported	
Haematuria				If reported	If reported	If reported	If reported	
Pelvic Pain VAS				If reported	If reported	If reported	If reported	
Return to Normal				X	X (if not previously achieved)			
Patient Satisfaction				X	X	X	X	
Subject Interview								
Medical History	X							
Concomitant Medications	X	X	X	X	X	X	X	
Voiding Assessment				X	X	X	X	
Intervention Review	X		X	X	X	X	X	
Testing								
Freestanding uroflow; PVR^3			X	X	X		X	
Urinalysis (UA)	X			X	X		X	
Urine Culture and Sensitivity	If indicated			If indicated	If indicated		If indicated	
Investigator Completed								
DRE	X				X		X	
Urodynamics	X 						X	
US	X 							
Cystoscopy (flexible)	X 						X	
Procedure		X						
Catheterisation Review	X	X	X	X	X	X	X	
Trial Without Catheter (TWOC)			X 					
Adverse Event Review		X	X	X	X	X	X	
Subject Discontinuation								X

 Office or phone visit acceptable. If subject returns to clinic due to an AE, any testing will be entered in EDC as interim (if outside visit window).

 Relevant medications and interventions only: BPH, LUTS; Sexual Function; GU; Prostate Cancer.

 Uroflow strip chart recordings, abnormal UA and urine culture results, urodynamics reports, and cystoscopy videos collected in the study will be retained as a part of the dataset and must be redacted.

 Can perform day of procedure prior to (index) UroLift procedure to reduce site and subject burden.

 TWOC should be repeated per standard of care if first attempt unsuccessful.

 Urodynamics testing may be performed at each study site if a testing facility is available and a qualified operator is on-site.

## 10.14 Performance of Study Procedures

---

### 10.14.1 Lab tests

A urinalysis will be collected and analysed from an accredited and certified laboratory. Redacted abnormal urinalysis results and urine culture results will be uploaded into the EDC system. Documents supporting laboratory credentials along with normal ranges should be kept in study files. Urinalysis (UA) should be collected within 30 days prior to index procedure. As subjects in screening will be on a catheter due to urinary retention, UA results cannot be used exclusively to determine eligibility. Urinary tract infections and gross haematuria should be based on the medical opinion of the investigator and may supersede lab results. UA may be performed by dipstick or microscopic analysis. Urine cultures should be performed if UA abnormal, clinically significant and indicates a urinary infection. Digital rectal exam (DRE) should also support the investigator decision to enrol and detect abnormalities in follow-up.

### 10.14.2 Transrectal or Transabdominal Ultrasound

Transrectal ultrasound (TRUS) or abdominal ultrasound shall be performed to assess eligibility for prostate volume ( $\leq 100\text{cc}$ ) and rule out enlarged median lobe (or “middle lobe”). In general, an intravesical prostatic protrusion (IPP) should be viewed under cystoscopy to rule out enlarged median lobe. Additional measurements will be taken to characterise the prostate including length, transverse width, and anterior/posterior width. The ultrasound procedure can be performed in advance or on index procedure day. Results will be recorded on an eCRF. Exams that were performed prior to screening but within 6 months of the index procedure, may be used instead of repeating for the study, provided there is source documentation.

### 10.14.3 Cystoscopy

A flexible cystourethroscopy (cystoscopy) shall be performed to determine eligibility for urethral tortuosity or strictures (i.e. ability to insert a 20F sheath), prostate and bladder neck morphology, calculus urinary, and presence of an enlarged median lobe contributing to obstruction. A pre-procedure cystoscopic visualisation may be performed to qualify for the study provided the subject is aware of the potential for not meeting enrolment criteria. The cystoscopy should be performed while digitally recording, and should adequately visualise the bladder, the full prostatic urethra, and bladder neck. An additional cystoscopy after

implant placement shall be performed to rule out the presence of protruding or exposed implants.

#### 10.14.4 Urodynamic testing

Urodynamics are now widely accepted as the reference standard to determine the grade of bladder outlet obstruction (BOO) and to assess detrusor contractility function. It is of particular interest to characterise the contribution and extent that each participant is in the AR disease state. Urodynamics testing may be performed at each study site if a testing facility is available and a qualified operator is on-site.

To ensure consistency across visits, the equipment used for study procedures will have documented calibration per manufacturer standards that is copied to study files. Detailed urodynamic procedure will be outlined in the manual of operations (MOP).

#### 10.14.5 Freestanding Uroflowmetry

Subjects will be asked to refrain from voiding for two hours prior to uroflow testing. Uroflowmetry shall be obtained with the subject in a standing position prior to any instrumentation. A bladder scan is recommended to be performed prior to voiding to assure that the subject has a bladder volume of at least 250 mL. Site should ensure the subject has a full bladder to increase the validity of the uroflow. Results will be recorded for each void in the eCRF and redacted waveform strip recordings uploaded in the electronic data capture system.

There are several potential flows that would require over-read including spikes or rapid fluctuations in the uroflow curve. These aberrations are commonly caused by mechanical disturbances of the flow sensor and abdominal straining either during or at the end of the void. If the Investigator is of the opinion that the machine read peak flow rate is an artifact and that the peak flow rate should be over-read by applying the 2 second-rule, the Investigator may use standardised methodology.

Detailed over-read procedure will be outlined in the manual of operations (MOP).

#### 10.14.6 Post Void Residual Urine Volume

Following freestanding uroflow, residual urine volume in the bladder shall be assessed by bladder scanner or abdominal ultrasound. Only post void residual urine volume visualised after the valid uroflow shall be used for analyses.

## 11 Electronic Case Report Form (eCRF) Entry

---

The Sponsor will provide optional source worksheets in an organised, tabbed binder to facilitate capture of protocol required data. Medical records from Institution and source worksheets will be entered into an online electronic data capture (EDC) system hosted by MedNet, Inc. The EDC System and its eCRFs will be built by the Sponsor and undergo validation and testing prior to launch. Each user will undergo documented training and must be a part of the delegation of authority log. The EDC System requires a personal password that expires every 90 days, automatically logs out after 90 minutes, and since U.S. based, is 21 CFR part 11 compliant. Modifications of data fields will be kept to a minimum, but if an unforeseen error or amendment to protocol demands a change, the system features ability to update in short time.

Data entry should occur in a timely manner for accuracy, but additionally for complying with regulations if unanticipated or serious adverse event occurs. Further, the EDC System will be used by Sponsor to plan monitoring, issue payments, device resupply, and to control the study minimum and maximum enrolment thresholds. See the entry time deadlines per data type below (**Table 8**).

**Table 8 eCRF Entry Timely Target**

eCRF Data	Entry Time
• Screening Forms and questionnaires	Within 14 Days
• Index Procedure Forms	Within 48 Hours
• Device Performance Issues with clinical sequelae	Within 24 Hours of knowledge of event
• Serious Adverse Event Form (includes Unexpected Adverse Events)	Within 24 hours of knowledge of event
• Subject Death	Within 24 hours of knowledge of event
• Follow-up Forms & questionnaires	Within 14 Days
• Other Forms (Protocol Deviation, etc.)	Within 14 Days

## 12 Data Collection and Confidentiality

---

Qualified trial staff at each site will perform primary data collection drawn from source document (hospital chart) review. Sponsor designated monitors will perform clinical monitoring, including review of eCRFs with verification to the source documentation.

All investigators and study site staff must comply with the requirements of the General Data Protection Regulation (GDPR) with regards to the collection, storage, processing and

disclosure of personal information and will uphold the regulation's core principles. This will be completed as follows:

- Personal information will be collected and stored in secure locations at the site
- Participants will be given a site number followed by participant number to ensure data is coded and depersonalized
- Access to the EDC system will be limited
- Data will be transmitted via an EDC system
- Media will redact any personal information before being transferred to Sponsor

## 13 Risks and Benefits of PUL and the Clinical Investigation

---

### 13.1 Anticipated clinical benefits

There are no guaranteed benefits from participation in this study. Extensive clinical experience with the UroLift System, in absence of urinary retention, has established the safety of the procedure and effectiveness of the UroLift System. For those subjects who suffer from acute urinary retention and BPH, the UroLift System has the potential to address their condition without heating, burning, or cutting tissue. The UroLift System has received CE Mark in Europe, allowing it to be marketed to the United Kingdom. In published clinical studies, it has been shown to significantly reduce LUTS rapidly while preserving important functions, such as sexual function and continence.

Because the PUL procedure takes a prostatic tissue sparing approach rather than tissue resection or ablation, there are potential benefits over conventional surgical treatments for BPH. There is a potential that the PUL procedure requires less anaesthesia and causes less bleeding and sexual dysfunction than more invasive modalities such as transurethral resection of the prostate (TURP) or laser resection. There is a potential that there may be a decrease in procedure time, catheter time, and/or post-operative recovery time when compared to other surgical therapies. There is potential that the time waiting for a procedure while catheterised is reduced. Information gained from this study may be used to benefit future subjects and help guide their therapy.

### 13.2 Anticipated Adverse Events

---

Adverse events will be solicited from the subject and documented after enrolment (see section 14 Adverse Events) the UroLift System Treatment, and at each follow-up time point. The risks of the undergoing the PUL procedure as part of this study are the same as having the procedure without being in the study.

Possible anticipated adverse events may be, but are not limited to those symptoms or events related to the disease process, the procedure (Section 13.3), device use (Section 13.5), reactions to medication inclusive of anaesthesia, and/or the study testing.

Anticipated adverse events that are: (1) reflective of the disease process (such as exacerbation of LUTS) and/or (2) inherent to this and any prostatic invasive procedure and expected to occur in this subject population are still to be reported as AEs during this study.

### 13.3 Anticipated Procedural Adverse Events

---

Possible anticipated complications related to procedure, anaesthesia and medication include, but are not limited to: death, damage to non-urinary systems, surgical trauma, bleeding, catheter misplacement, allergic reaction, decrease in kidney function, pulmonary embolism and infection.

### 13.4 Protocol Required Testing with Anticipated Adverse Events

---

Possible anticipated adverse events related to urodynamic testing are discomfort passing urine, urgency, frequency, bladder spasms, lower urinary tract symptoms, haematuria, and urinary tract infection.

### 13.5 UroLift System Adverse Events

---

Possible adverse events related to UroLift PUL include but are not limited to:

Adverse tissue reaction or allergic response  
Bleeding associated with the urinary tract, gastrointestinal tract, pelvic region or abdomen  
Change in urine control muscle function or narrowing of the urine path  
Changes in ejaculation such as semen going into the bladder rather than out the end of the penis (retrograde ejaculation), inability to ejaculate (anejaculation), reduced ejaculation volume, delayed ejaculation, change in ejaculate characteristics, blood in semen (hematospermia), and pain with ejaculation  
Cloudy urine, discharge, bleeding (haematuria), proteinuria, or blood clots in urine that may require a catheterisation with or without fluid irrigation of the bladder and urethra (bladder irrigation or evacuation)  
Equipment malfunction or device failure such as broken needle or device associated with undesirable clinical sequelae  
Elevated PSA  
Foreign body in patient and associated problems including foreign body sensation, erosion, inflammation, or irritation

---

 Complications listed in this section were identified through Sponsor risk management files and include both reported and theoretical risks; the majority of AEs reported through Sponsor's clinical studies were mild or moderate and transient in nature (See Sections 5.1.2. and 5.2)

Embolization of foreign body or blood clot  
Gastrointestinal (GI) damage or changes including rectal damage, blockage or narrowing in rectum, fistula creation, hemorrhoid creation, hemorrhoidal pain, bleeding from the GI tract, constipation, diarrhea, vomiting, inability to control bowel movements (rectal incontinence), and additional procedure.  
Improperly placed implant, including those that are not removable  
Inability to urinate requiring a catheter be put in (urinary retention requiring a catheter)  
Increased, returned, or failure to improve lower urinary tract symptoms  
Having to urinate several times at night (nocturia)  
Hypotension or hypertension  
Weak urine stream  
Sudden urge to urinate (urgency)  
Frequency of having to urinate  
Urinating small amounts  
Straining to urinate  
Spraying of urine when going the bathroom, splitting of urinary stream  
Difficulty starting or continuing to urinate (urinary hesitancy/ intermittency)  
Sensation of not emptying bladder, feeling of incomplete emptying  
Incomplete emptying of bladder, increased residual urine  
Dribbling after urination  
Infection such as urinary tract infection (bacterial colonisation, leukocyturia, sepsis), epididymitis, orchitis, and prostatitis  
Stones (calculi) or encrustation on the implant or in the prostate, bladder or other parts of the urinary tract  
Pain or discomfort during urination (dysuria)  
Pain, tenderness, discomfort, spasms, or burning sensation in areas such as the lower abdomen, back, penis, prostate, scrotum, groin, perineum, urinary tract, bladder or pelvic region associated with undesirable clinical sequelae  
Urine leakage (incontinence)  
Urinary tract irritation, inflammation, edema, swelling, change in function and compromised function (including kidney, ureter, bladder, prostate, urethra, and penis)  
Prostate abnormalities and damage  
Puncture of, problems with, injury or damage to the urinary system, bladder, ureter, ureteral orifice, trigone, bladder neck, urethra, or nearby structures including but not limited to false passageway creation, blockage, trabeculation, stricture, adhesion, stenosis, contracture, reduced sensation, spasm and requirement of additional procedure or medication.  
Puncture, injury or damage to nerves or neurovascular bundles resulting in foreign body response, erectile dysfunction, pain, reduced sensation, or requirement of additional procedure or medication.  
Prostate, bladder, urinary tract or GI tract hyperplasia, dysplasia, neoplasia or polyp formation  
Pyrexia  
Reproductive system disturbances such as infertility, decreased potency, impotence, erectile dysfunction, pain with erection, penile damage, penile disorder, penile numbness, decrease or loss of sexual desire (libido), loss of orgasm  
Requirement for delayed, aborted, changed or additional procedure

## 13.6 Possible Interactions with Concomitant Medical Treatments

---

There are no anticipated interactions with concomitant medical treatments. It is recommended that the subject is cleared to discontinue anticoagulant therapy for a period of at least three days prior to surgical intervention unless subject is on maintenance dose of aspirin ( $\leq 100\text{mg}$ ).

## 13.7 Possible Risks of Participation in a Clinical Trial

---

There are standard risks of participating in a research study given potential of accidental disclosure of subject's confidential information. Every effort will be made to ensure that subject personal information remains confidential at all times including application of Subject ID and redacting personal information before submitting to Sponsor.

## 13.8 Risk Mitigation

---

Clinical risks will be minimised by careful assessment of the subject prior to, during, and after the procedure. Careful follow-up will help minimise risks associated with changing conditions of the subject. Proper subject selection will be achieved by following the subject inclusion and exclusion criteria. Participating Investigators are highly experienced UroLift operators and experienced in clinical research. The study centres have adequate resources and facilities to safely conduct study with compliance.

The UroLift System itself has safety features. The delivery device can't be deployed without switching the safety trigger off and features a bypass suture cutting mechanism. Users are able to manually retract needle if necessary. All of these features are detailed in the instructions for use.

## 13.9 Risk-to-Benefit Rationale

---

The UroLift System is CE marked for use in the United Kingdom. The potential clinical risks in subjects with acute urinary retention have been minimised through the selection criteria for appropriate subjects, experienced investigators (minimum of 30 PUL and seasoned researchers), and prior pre-clinical and clinical testing of the UroLift® System. The analysis shows that the potential subject benefits outweigh the potential risks to the subject. This study will be conducted ethically and in adherence to regulations.

The design of the feasibility study is qualitative, yet with the rigorous data point collection and reasonable sample size, it is expected to provide clinically meaningful information. The goals are twofold, the first to assess initial effectiveness and safety; the

second, to optimise the study design for a larger, significantly powered, randomised trial. The first goal will be supported by the primary endpoint, which is the most accepted surrogate for effective retention resolution. The follow-up schedule is also comprehensive, with five visits through 1 year to gauge the related safety profile, and, the maintenance of voiding without catheter. The benefit of offering UroLift as an alternative option to invasive surgery may be recognised with the comparison to the matched dataset of invasive treatment. The potential for optimising future study design and conduct is increased by including multiple sites, each experienced in UroLift and clinical research, which service a large BPH population.

## 14 Adverse Events

---

### **The following definition is from the ISO 14155 standard.**

An adverse event (AE) is defined as any undesirable medical occurrence in a clinical trial subject, whether it is considered to be related to the device or not, that includes a clinical sign, symptom, or condition.

#### 14.1 Serious Adverse Events

---

Serious Adverse Event (SAE) is defined as untoward occurrence that:

- (a) results in death;
- (b) is life-threatening;
- (c) requires hospitalisation or prolongation of existing hospitalisation
- (d) results in persistent or significant disability or incapacity;
- (e) consists of a congenital anomaly or birth defect; or
- (f) is otherwise considered medically significant by the investigator.  
(in-patient hospitalisation is at least 24 consecutive hours)

#### 14.2 Unexpected Adverse Event

---

An unexpected adverse event is an event which by nature, incidence, severity or outcome has not been identified in the current version of the Sponsor risk management files.

#### 14.3 Not an Adverse Event

---

Any reoccurrence of urinary retention will not be considered an adverse event, but clot retention that may lead to urinary retention will be considered an adverse event.

Any colonization of subjects requiring catheter deemed not clinically significant will not be considered an adverse event.

The need for any alternative procedure is not considered an AE or SAE, however the diagnosis or symptoms that led to repeat procedure could be. If the alternative procedure involves either (a) hospitalisation greater or equal to 24 hours *longer* than the timeframe that is standard of care for that procedure at that site, or (b) an unexpected outcome then it will be recorded as an SAE.

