## 6.3 Primary Safety Assessment

---

Rate of serious adverse events (SAEs) related to BPH intervention through 3 months.

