### 15.8.3 Post-procedure

The following post-surgery data will be collected for period after discharge through 12 months after their surgical intervention (if available):

• Date of contacts	• Type, reason of contact (phone, office visit)	• Complications, adverse events (urological, sexual function, cancer and SAEs)	• Interventions
• BPH medications, indication	• Symptom scores	• Uroflowmetry/PVR	• Catheterisations

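### Section 14.3 takes recurrent urinary retention (other than clot retention) out of the adverse events, contrary to 13.2 and 14.1, and leaves a serious retention episode no stated route into the primary safety rate

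*Combined protocol and SAP*

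**What the plan says.** Section 14.3 states that "Any reoccurrence of urinary retention will not be considered an adverse event". The same sentence makes one exception: "clot retention that may lead to urinary retention will be considered an adverse event". Section 10.10 carries the rule into data collection. It asks for the adverse event behind a secondary intervention, excepts urinary retention, and refers the reader to 14.3.

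Three other sections point the other way:
- Section 13.2 says that anticipated events reflecting the disease process, or inherent to a prostatic procedure and "expected to occur in this subject population are still to be reported as AEs during this study".
- Section 13.5 names retention needing a catheter among the possible adverse events of PUL.
- Section 14.1 defines an SAE as an untoward occurrence that meets any of several criteria. One is that it "requires hospitalisation or prolongation of existing hospitalisation", with the note that "in-patient hospitalisation is at least 24 consecutive hours". Retention is not exempted.

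The primary safety assessment in 6.3 is "Rate of serious adverse events (SAEs) related to BPH intervention through 3 months". Section 16.6 (Retrospective Arm) also compares related AEs and SAEs between the PUL subjects and the retrospective surgical patients.

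**The concern.** All the men are treated because they are in retention, so its return is a foreseeable way for the procedure to fail. If a man is readmitted for more than a day with retention, 14.1 makes that an SAE and 13.2 makes it reportable, but 14.3 says it is not an adverse event at all. A site cannot follow both 13.2 and 14.3.

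Three results depend on which section is followed: the primary safety rate in 6.3, the related SAEs examined in the review after the first 15 subjects (16.1), and the between-arm comparison of related AEs and SAEs in 16.6.

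**Working it through.** The plan gives no expected SAE rate, threshold or power for the safety assessment, so there is no figure to reproduce. The check is to follow a retention episode through the reporting rules and then to scale the effect.

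**1. Route of a retention admission of 24 hours or more**
- Section 14.1: it meets the hospitalisation criterion.
- Section 14.3: it is not an adverse event unless it is clot retention.
- Section 14.5: the sponsor is notified of an SAE by completion of the AE form in the data capture system. An event that is not an AE has no stated reason to be entered there.
- Section 14.6: the independent reviewer adjudicates reported adverse events, including whether they are serious and related. An unreported episode does not reach the reviewer.
- Section 10.10: if the episode leads to another intervention, the form still does not ask for retention as an adverse event.
- Section 6.3: the numerator is related SAEs. No text adds retention admissions back.

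The first sentence of 14.3 says only that retention is not an adverse event. Its third paragraph, on alternative procedures, mentions both AEs and SAEs. That retention also leaves the SAE count is therefore an inference, but the reporting route makes it a strong one. The third paragraph also allows that the diagnosis behind a repeat procedure could be an AE or SAE, which the first sentence denies when that diagnosis is retention.

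**2. Direction and size**

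Take the rate as the proportion of men with at least one related SAE, with the maximum N of 55 (Section 7). Let *a* be the men with a related SAE of another kind within 3 months. Let *k* be the further men whose only related SAE in that period is a retention episode.

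- Rate under 14.3 = *a*/55
- Rate under 14.1 with 13.2 = (*a* + *k*)/55
- Difference = *k*/55, which is never negative; 1/55 = 1.8 percentage points for each man

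For illustration with *a* = 0 and exact (Clopper-Pearson) 95% intervals, where *k* is assumed:

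| *k* | Rate if counted | 95% interval |
|---|---|---|
| 0 | 0/55 = 0% | 0 to 6.5% |
| 1 | 1/55 = 1.8% | 0.0 to 9.7% |
| 2 | 2/55 = 3.6% | 0.4 to 12.5% |
| 3 | 3/55 = 5.5% | 1.1 to 15.1% |

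Under 14.3 each of these rows would be reported as 0/55.

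The chance that at least one event is omitted is 1 − (1 − p)^55, where p is the chance that a man has a related retention SAE within 3 months. The documents give no p. At assumed values of 2%, 5% and 10% the result is 67%, 94% and 99.7%, with 55 × p = 1.1, 2.8 and 5.5 expected events.

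**3. The two arms**

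Sections 15.8.2 and 15.8.3 have abstractors collect urological adverse events and SAEs, where available. Catheterisations and interventions are separate items. Section 15 does not say whether the 14.3 exclusion applies to this abstraction, and 14.3 does not say which arm it covers. The rule for the comparator is therefore unstated.

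**The case against.** The strongest defence is that 14.3 is the specific rule and a coherent one. Table 2 and Section 14.4 count only new or worsened conditions as AEs, and every man enters in retention, so its return can be read as non-response. Section 13.2 is general and itself points to Section 14. Section 13.5 is a risk list that includes theoretical risks, not a reporting instruction. Retention is also not hidden: 16.6 gives it a Kaplan-Meier analysis in the safety population and between-arm recurrence rates, catheterisation is reviewed at each visit, and 10.11 has an independent urologist judge treatment failure. There is no success criterion (16.7).

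Much of this stands. Retention belongs among the effectiveness outcomes, and no formal decision turns on the SAE rate. But the protocol does not give this reason for 14.3, and retention after a successful void could be called new onset. None of the separate analyses identifies which episodes were serious, so they cannot restore the 6.3 count.

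A reader might infer three stronger things that the documents do not support:
- **That no retention-related admission can ever count.** Clot retention is excepted. A separate diagnosis at the same admission can be an SAE. So can an alternative procedure with an unexpected outcome or a stay at least 24 hours beyond that site's standard.
- **That retention is counted in the surgical arm and dropped in the PUL arm, which favours PUL.** No text says it is kept in the retrospective AE count. Listing recurrence as its own outcome for both arms may suggest the opposite. Retrospective events are collected only where available, while PUL subjects are asked at each visit, so the net direction cannot be stated.
- **That the shortfall can be put at a definite number of points.** The documents give neither a recurrence rate nor a serious fraction. Only related events enter 6.3, and Table 9 lets an event explained by underlying disease be rated unlikely or not related.

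**Conclusion.** The conflict is real and lies in current text. Sections 14.3 and 10.10 remove recurrent retention other than clot retention from the adverse events, while 13.2 and 14.1 would report it and, if serious, class it as an SAE. As written, an episode that is serious in its own right has no stated route into the primary safety rate.

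The effect on that rate is one-sided: zero or downward, by 1.8 points for each affected man at N = 55. This assumes that the rate is a proportion of men, that the episode is judged related, and that the man has no other counted SAE. The number of such men is unknown. For the between-arm comparison, the conclusion is only that the rule is unstated and retention may be counted differently by arm.

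This should be corrected. It bears on the named safety result and on what a later trial would take from it, not on a pass or fail decision.

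**What to change.** Reconcile 10.10, 13.2, 13.5, 14.1 and 14.3 as follows:
- Keep recurrent retention as an effectiveness outcome, and say in 14.3 that this is the reason it is not routinely an AE.
- Add that any retention episode meeting a 14.1 criterion is recorded as an SAE, adjudicated for relatedness under 14.6, and counted in 6.3 if related within 3 months. Amend 10.10 to match.
- State in Sections 15 and 16.6 one retention rule for both arms, or show the AE and SAE comparison with and without retention in both arms.

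The cost is a few sentences of protocol text, minor changes to the AE form and the abstraction instructions, and a matching line in the Safety Plan that holds the adjudication conventions. The reported SAE rate may be slightly less favourable. Treatment and visits do not change.
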